### METHODS

#### Study design

This is a multi-centric, randomized, active-controlled, non-inferiority trial. Stratification of subjects is done according to center and birth weight.

### **Eligibility**

All neonates whose birth weight is more than 1000 grams with clinically suspected sepsis for which the treating physician decides to start antibiotics will be eligible for screening.

# Inclusion Criteria

Subjects should satisfy all the following criteria:

- Neonates aged 0-28 days, either inborn or out born, who are currently admitted in the Neonatal unit of the centre,
- Whose birth weight is greater than 1000 grams (it should be reliably ascertained from records of a hospital.
- Whose residence is within approximately 15 kms from the centre, so that the infant can be brought back to the centre for follow up.
- Who have suspected septicemia for which a conventional or BACTEC/BACTALERT blood culture is sent and for which the treating physician decides to start antibiotics.

#### **Exclusion Criteria**

- Central Nervous System infection (meningitis will be defined as CSF Cells >25 per uL with polys >60%OR [(CSF glucose <20 mg/dL OR CSF:blood\* glu ratio <0.6) AND (CSF protein >150 mg/dL in term OR >180 mg/dL in preterm)]
- Septic arthritis, osteomyelitis or deep-seated abscess as clinically judged by the treating team
- Life threatening congenital malformations as judged by the principal investigator of the centre

Parents of the subjects who satisfy the eligibility criteria are approached for participation in the study. They are provided a Patient Information Sheet for Enrolment (Appendix 1) and the nature and purpose of the observational part of the study will be discussed with them and they will be informed that they may be approached again for the randomized controlled trial portion of the study after approximately 7 days or more, if the infant meets criteria for randomization. The patient information sheet will also be discussed with the parents in a non-technical language. Written informed consent (3 copies) for enrolment will be taken from a parent in the presence of a witness (Appendix 2). One copy will be handed to the parent, one will be kept with the investigator and 1 will be kept in the hospital records. There will be no restrictions on the parent's right to ask questions related to the study. Patient-related data from start of screening up to eligibility for enrolment will be recorded in the "Screening sub-form" of Proforma A of case report form.

### Data of observational part of the study

After obtaining consent for enrolment, the following data will be recorded: maternal and neonatal demographic data, maternal risk factors of sepsis, clinical and laboratory features of sepsis, culture and sepsis screen reports, antibiotics and their doses. The subjects will be followed up on a daily basis for remission of clinical signs (using a standard list of objectively defined signs), change of antibiotics (if any, with reasons), and co-interventions- Decisions regarding the kind of antibiotics and changes, if any, from the point of enrolment to the point of randomization will be left to the judgment of the treating physician.

Each of the participating Centres will decide on the empirical antibiotics based upon their standard empirical antibiotic policy. No changes in policy will be made for the sake of the research study. The antibiotics shall be stored, prescribed and dispensed as per the recommendations of Neofax essentials, 2014. All study subjects will receive routine care as per guidelines of the concerned centre.

# Randomization criteria

Randomization will be done at the end of the 7th day of therapy with sensitive antibiotics. Of the enrolled subjects, only those who satisfy the criteria below will be randomized:

# Eligible for randomization

- Positive blood culture other than *Staphylococcus aureus*
- No signs and symptoms of sepsis from end of day 5 through end of day 7 of starting sensitive antibiotics (This will be on day 5 through 7 for those who have improved and will be day 8 through 10 for those where in empiric antibiotics have been resistant requiring a change in antibiotic on day 3 of enrolment)

# Not eligible for randomization

- Sterile blood culture
- Suspected contaminants in blood culture.
- Growth of Staphylococcus aureus in blood culture
- Growth of fungal organism in blood culture
- Diagnosis of meningitis, septic arthritis, osteomyelitis, abscess
- Has not gone into remission on day 5 or have recurrence of symptoms from day 5 through day 7
- If the empiric antibiotic is resistant but neonate has shown improvement of signs and symptoms of sepsis and there is ambiguity regarding in vivo sensitivity of antibiotic use

These elaborate criteria have been drawn up because this is an equivalence (non-inferiority) trial. In an equivalence trial, extra care has to be taken to exclude subjects who are likely to respond irrespective of which treatment arm they are in and also subjects who are not likely to respond irrespective of which treatment arm they are in. This is because inclusion of such patients would bias the results towards no effect (ie equivalence).

Data from enrolment until the point of determining eligibility for randomization will be recorded in the "Enrolment sub-form" of Proforma A of the case report form.

## **Randomization**

Those eligible for randomization will be approached for consent for randomization. Parents will be provided Parent Information Sheet for Randomization (Appendix 3) and the details of the Randomized Controlled Trial will be discussed with them. Written informed consent (3 copies) for randomization will be taken from a parent in the presence of a witness (Appendix 4). One copy will be handed to the parent, one will be kept with the investigator and 1 will be kept in the hospital records. Subjects whose parents give consent for randomization will be randomly allocated to one of 2 groups:

Group A: Antibiotics will be stopped at the end of day 7.

Group B: The same antibiotics will be continued for a total of 14 days.

Those who do not satisfy the criteria for randomization and those whose parents do not give consent, will not be randomized and they will be followed up daily until clinical signs remit and will be administered the standard 14 days course of antibiotics.

#### Randomization procedure

Stratified, block randomization will be employed as described above. Randomly varying block sizes will be used and size of the blocks will be concealed until the end of the study. Each block will have equal number of allocations to Group A and Group B in a random sequence. Stratification will be by birth weight (1000-1499, 1500-2000g and >2000 g) and by Centre. Random number lists generated from a website http://randomizer.org will be converted into the sequence of allocation to the 2 Groups. Concealment of allocation

Slips bearing the allocated Group will be placed in opaque envelopes, which will be sealed and numbered serially on the outside. There would be separate sets of such envelopes, one for each stratum (ie Center and birth weight group). In each center, envelopes will be opened in serial order, as each subject is included in the study. The name and identification details of the subject will be written on the outside of each envelope and all envelopes will be returned to the Principal Investigator in the nodal center.

#### Intervention

Among neonates who are allocated to group A, antibiotics will be stopped on day 7 of sensitive antibiotics (ie. immediately after randomization).

Among neonates who are randomized to group B, antibiotics will be continued until day 14 (ie for 7 more days after randomization).

If either of the groups develops signs and symptoms of sepsis, these babies will not be discharged, investigations will be done and appropriate antibiotics will be started. Each Centre will administer empirical antibiotics based upon their standard empirical antibiotic policy. No changes in policy will be made for the RCT. The antibiotics shall be stored, prescribed and dispensed as per the recommendations of Neofax essentials, 2014. All study subjects will receive routine care as per guidelines of the concerned centre.

#### Blinding

The following research team members will be blinded: the adjudicators of outcome and the laboratory personnel. The following will be unblinded: the principal investigator, the research staff, nurses and resident doctors involved in the care of the subjects in hospital. Data related to assessment of the outcomes will be recorded in a separate detachable part of the proforma (Proforma-part B). The pages of the proforma of a patient will have a unique identification number. Part B will be detached from the main proforma and handed to the adjudicators.

#### Follow-up

Any further hospitalization after stoppage of the antibiotic course would be at the discretion of the treating unit.

The follow-up period will extend from the point of randomization for 5 weeks (35 days). Details of all episodes of illness during this period (whether in hospital or after discharge) will be filled by the research staff. At the time of discharge, parents of all the babies will be given cards with the Investigators' names and contact information printed on them. Parents will be asked to report to the Newborn Unit for each episode of illness during the follow up period. Pediatric Emergency staff and Outpatient Department staff will also be informed about the special cards and asked to inform the Investigator in case such a baby reports for any illness.

In addition, all the babies will be followed up in the premises of the newborn unit at 48 hours ( $\pm$  12 hours) for any signs of a sepsis syndrome. If the parents do not bring the baby for follow-up, the research staff will make a home visit. In addition, parents will be asked to bring the baby back to the Follow-Up Clinic by appointment on a weekly basis ( $\pm$  2 days) for 35 days after randomization with particular emphasis on the visit at 28 days and 35 days. At each visit questions will be asked by the assessment team to ascertain whether an episode of a sepsis syndrome has occurred in the preceding week that required antibiotics. If the parents do not bring the baby back for weekly follow-up, the research staff will make a home visit.

Complete addresses & telephone numbers of the patients will be taken before discharge and babies who do not report in will be contacted at their homes.

All episodes of illness in a 35-day period after randomization will be evaluated for antibiotic treatment failure. A blood culture and sepsis screen (C reactive protein, complete blood counts,), procalcitonin, chest X-ray and CSF examination will be done, depending on the discretion of the treating physician. All clinical and laboratory details related to the episode of illness will be recorded on Proforma part B, detached and handed over to a blinded Neonatologist (adjudicator) to determine whether the episode qualifies to be a relapse of sepsis. In case any radiological imaging is performed, either digital (preferable) or hard copies of the images will be sent to the blinded Neonatologist at the nodal Centre after removing patient identifiers. In the event that the subject could not be brought back to the unit for the episode of illness, and treatment was received outside, every effort will be made by the assessment team to contact the treating physician and ascertain all details and such details will be entered in pro forma part B. Photocopies of lab reports and notes of other physicians will also be sent to the blinded neonatologist, after removing patient identifiers. Proforma part B will not contain any information by which the group of randomization may be ascertained.

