### Secondary outcomes

"Definite relapse" and "probable relapse" will be separate secondary outcomes, each assessed at 21 days and 28 days after antibiotic completion. [This was originally "definite or probable relapse"].

Episodes of relapses (# 1-4) will be analyzed both as per protocol and as per intention-to-treat:

1. "Definite relapse": by 21 days after antibiotic completion.

2. "Probable relapse": by 21 days after antibiotic completion.

3. "Definite relapse": by 28 days after antibiotic completion.

4. "Probable relapse": by 28 days after antibiotic completion.

Episodes of relapses (# 5-7) will be analyzed as per intention-to-treat:

5. "Definite or probable relapse" in the 28-day period after randomization and 35-day period after randomization

6. "Definite" in the 28-day period after randomization and 35-day period after randomization

7. "Probable" in the 28-day period after randomization and 35-day period after randomization]

The following will also be analysed in the 35-day period of observation after randomization:

(A) Episodes of secondary infections during the observation period. These may be bacterial or fungal.

(B) Adverse events: All fresh adverse events occurring after randomisation would be recorded. Adverse events with onset prior to randomisation would be recorded only if there is worsening after randomisation. Adverse events are listed and defined as per Appendix 5.

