### **Sample Size Calculation**

The sample size was calculated to be 350 in each arm based on the following assumptions: Event rate for the composite primary outcome of "definite or probable relapse" assumed to be 10% (combining both 7- and 14-day treatment arms) based on the earlier study (Chaudhary G, Dutta S, Narang A, Journal of Tropical Pediatrics 2006), non-inferiority margin of 7%, one sided alpha level as 5% and power of 90% and loss to follow- up of approximately 10%.

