Title:

Comparison of the Efficacy of a 7-day Versus 14-day Course of Intravenous Antibiotics in the Treatment of Uncomplicated Neonatal Bacterial Sepsis: a Randomized Controlled Noninferiority Trial

NCT number: NCT 03280147

Date of document: 26 September 2019

STATISTICAL ANALYSIS PLAN

The baseline variables shall be described using descriptive statistics. Categorical variables will be described by percentages. Numerical variables will be described as mean (standard deviation) or median (1st, 3rd quartile), depending on distribution. Normality of distribution of numerical variables will be tested by Shapiro Wilk test and QQ plot.

The primary outcome variable is "definite or probable relapse" within 21 days after stopping antibiotics. Secondary outcome variables include individually definite and probable relapse within 21 days and 28 days after stopping antibiotics; definite and probable relapse within 28 days and 35 days after randomization; "definite or probable relapse" within 28 days and 35 days after randomization; secondary bacterial infections within 35 days after randomization and adverse events within 35 days after randomization. Analysis will be both per protocol as well as intention-to-treat, as this is a noninferiority trial.

As all the outcome variables are categorical, chi-square test with Yates correction or Fisher's Exact test, as applicable, will be used to compare the 2 groups.

Sub-group analysis has been planned for the following sub-groups: birth weight 1000-1499 grams, 1500 to 2000 grams, and >2000 grams, those infected with gram positive organisms versus the rest and those with radiological pneumonia versus those without radiological pneumonia. A p-value for the test of interaction (Breslow-Day test) will be derived for the subgroup analyses.

Multi variable logistic regression analysis will be performed to determine the relationship between group membership (7-day course of antibiotics versus 14-day course of antibiotics) and the primary outcome after adjusting for the following baseline covariates: birth weight, age of neonate, infection with gram positive organisms, number of days by which clinical remission of sepsis achieved prior to randomization.

Mid-term analyses will be performed by an independent Data Safety Monitoring Board at 1/3rd and 2/3rd of expected recruitment.

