Data Safety Monitoring Board will monitor serious adverse events in the trial. O'Brien-Fleming's stopping criteria will be used for the primary outcome while Pocock's stopping rules will be used for serious adverse events.

Analysis shall be done using the statistical software packages SPSS version 22.

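### Adverse events are compared over 35 days, but collection after discharge is specified only through a sepsis question and noticed illness, so mild and laboratory-detected events may be under-recorded in the arm discharged earlier.

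*Protocol*

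**What the plan says.** **Outcome and window.** Protocol, Secondary outcomes, item (B): "All fresh adverse events occurring after randomisation would be recorded". The period is 35 days after randomisation. The SAP lists "adverse events within 35 days after randomization" among the secondary outcomes and compares categorical outcomes by chi-square with Yates correction or Fisher's exact test. For interim monitoring it adds that "Pocock's stopping rules will be used for serious adverse events".

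**Treatment after randomisation.** Under Intervention, the 7-day group stops antibiotics at once and the 14-day group continues for 7 more days. The SAP title gives the route as intravenous. The per-protocol exclusions (Primary outcome variables) name lack of a cannula and unscheduled discharge as reasons for an incomplete second week, which implies inpatient care without stating it.

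**Stay after stopping.** Protocol, Follow-up: "Any further hospitalization after stoppage of the antibiotic course would be at the discretion of the treating unit".

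**Collection after discharge.** At the weekly visits, "questions will be asked by the assessment team to ascertain whether an episode of a sepsis syndrome has occurred in the preceding week", restricted to episodes that needed antibiotics. The 48-hour visit looks for signs of sepsis. The same section has research staff record every illness episode in or out of hospital, parents report each illness, and emergency and outpatient staff notify the investigator. The text after Follow-up adds that details of treatment received elsewhere are sought. Neither document gives an adverse-event checklist or a schedule for applying one.

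**Blinding.** Research staff and the clinical team are unblinded. The blinded adjudicator rules on relapse, not on adverse events.

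**The concern.** Appendix 5 has 48 numbered items. By my count about 16 are defined by, or usually need, a laboratory test: kidney injury, anaemia, cholestasis/hepatitis, low and high glucose, high and low sodium, high potassium, hyperbilirubinaemia, neutropenia, polycythaemia, thrombocytopenia, liver dysfunction, haemolysis, deranged coagulogram and disseminated coagulation. Arrhythmia is defined by ECG, and periventricular leukomalacia and intraventricular haemorrhage need imaging. Such events are found where infants are tested and watched, which is mostly in hospital.

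For up to 7 of the 35 days (7/35 = 20%) the arms may be observed in different settings, and the setting follows from the allocation. Any resulting bias favours the 7-day arm. A non-inferiority result on relapse is normally read alongside the harm comparison. If recorded harms are fewer with 7 days, the planned analysis gives the reader little means of judging how much of the difference is treatment and how much is observation.

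**Working it through.** **1. The plan's own figure.** From Sample Size Calculation: event rate "assumed to be 10% (combining both 7- and 14-day treatment arms"), "non-inferiority margin of 7%, one sided alpha level as 5% and power of 90"%, and "loss to follow- up of approximately 10"%.

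n = (1.645 + 1.282)² × 2 × 0.10 × 0.90 / 0.07² = 314.6, so 315 per arm; 315/0.9 = 350. The stated 350 per arm is reproduced. Nothing in this calculation depends on adverse events.

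**2. What the documents do not give.** They give no adverse-event rate, no detection probability and no length of stay for the 7-day arm. What follows is a sensitivity analysis on assumptions, not an estimate.

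**3. Model.** Assume the same true rate in both arms, 1 event per 100 infant-days, constant over 35 days; detection 100% in hospital and d at home; 14-day infants in hospital for days 0-7; 7-day infants in hospital for L days after randomisation. Expected recorded events per infant:

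- 14-day arm: 0.01 × (7 + 28d)
- 7-day arm: 0.01 × [L + (35 − L)d]

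The assumed rate cancels from the ratio of the two.

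| L (days) | d | 7-day | 14-day | Ratio 14-day/7-day | Infants with a recorded event, 7-day vs 14-day |
|---|---|---|---|---|---|
| 0 | 0.9 | 0.315 | 0.322 | 1.02 | 27.0% vs 27.5% |
| 0 | 0.7 | 0.245 | 0.266 | 1.09 | 21.7% vs 23.4% |
| 0 | 0.5 | 0.175 | 0.210 | 1.20 | 16.1% vs 18.9% |
| 0 | 0.3 | 0.105 | 0.154 | 1.47 | 10.0% vs 14.3% |
| 3 | 0.7 | 0.254 | 0.266 | 1.05 | 22.4% vs 23.4% |
| 7 | any | equal | equal | 1.00 | equal |

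The last column is 1 − exp(−expected events). It is the scale that the chi-square or Fisher test uses. At L = 0 and d = 0.3 the ratio there is 14.3/10.0 = 1.43, slightly below the 1.47 for events per infant.

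**4. Effect on the test.** Take a true 35-day risk of 20% in both arms, L = 0, 350 analysed per arm and a two-sided 5% test by normal approximation. With no bias, the chance of a significant result favouring the 7-day arm is 2.5%.

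| Timing of events | d | Recorded, 7-day vs 14-day | Chance of a false result favouring 7 days |
|---|---|---|---|
| Uniform | 0.9 | 18.2% vs 18.6% | 3.3% |
| Uniform | 0.5 | 10.6% vs 12.5% | 12.6% |
| Half the hazard in days 0-7 | 0.5 | 10.6% vs 15.4% | 48.0% |

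The planned Yates correction and about 10% loss to follow-up would lower these chances somewhat.

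**The case against.** The strongest answer is that follow-up is broader than the weekly question. A reader might infer that discharged infants are asked about sepsis and nothing else is collected. The documents do not support that: all illness episodes are to be recorded, through parents, emergency and outpatient staff, and outside physicians. This stands, and it confines the gap mainly to mild, asymptomatic and test-only events, which those routes do not reach because they start from illness that someone notices.

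Second, a reader might infer that the 7-day course is bound to look safer. Nothing says 7-day infants leave at randomisation. Stay is discretionary, infants in either group with signs of sepsis are kept in, and with equal stay the bias is zero. Immediate discharge is the extreme case, and with near-complete home detection even that gives about 2%. This stands too; the point is a risk of unknown size.

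Third, not every excess in the 14-day arm would be an artefact. Extravasation injury, thrombophlebitis or drug toxicity during a further week of intravenous treatment is a real effect of the longer course, and a count from randomisation rightly includes it. This also stands. It is a reason to show the components, not to remove events.

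Fourth, a reader might infer that the Pocock monitoring of serious events is undermined. Serious events are grades 3-5, mostly severe, treated or fatal, and harder to miss at home. They are not immune, since some grade 3 thresholds are laboratory values (sodium 161-170 mEq/L, platelets below 20,000), but no effect on the stopping rule has been shown.

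**Conclusion.** The point holds as a gap in how adverse events are ascertained and reported. Collection after discharge is not specified beyond the sepsis checks and noticed illness, the arms may differ in inpatient time for up to 7 of 35 days, and the SAP has no analysis that would reveal the consequence. Mild and laboratory-detected events may be under-recorded in the arm discharged earlier, in the direction that favours 7 days.

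The spurious excess in recorded events per infant runs from zero (equal stay, or equal detection at home and in hospital) through about 2% and 20% to 47% at 90%, 50% and 30% home detection. The non-zero figures rest on immediate discharge, full detection in hospital and a constant event rate, none of which the documents state. If events cluster in the first week after randomisation, the distortion is larger.

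This is a secondary safety outcome. The primary relapse outcome, its blinded adjudication and the 350 per arm are untouched. The change is worth making because it is cheap and because inpatient days, on which the size largely turns, are not among the planned tabulations.

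**What to change.** 1. **Protocol, Follow-up.** At the existing weekly visits, or the home visits that replace them, ask about the clinical Appendix 5 events as well as sepsis, with the same questions in both arms on the same schedule from randomisation, whether the infant is in hospital or at home.
2. **SAP.** Keep the full 35-day comparison of all adverse events. Add tables by days 0-7 and days 8-35 after randomisation, by grade, and by laboratory- or imaging-detected versus clinical events, with inpatient days per arm. State that any excess in the 14-day arm will be interpreted in the light of these tables.

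The first change narrows the gap for clinical events. It cannot find test-only events, and the second is there to show how far they drive the result. I would not restrict the main comparison to clinical and grade 3-5 events: that would take lower-grade renal and hepatic toxicity out of it, while laboratory-defined severe events would remain.

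**Cost:** a few more questions per visit and some extra tables. No new visit or test is needed, and the sample size does not change.
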